6.3.10 Concomitant Medication Assessments

A concomitant medication is any medication that the patient has been taking prior to enrollment and that the patient is expected to continue to take for some portion of the trial, as well as any medication other than the investigational product that the patient takes during the course of the trial.

The medications or treatment for controlling the ANCA-AAV must be recorded as concomitant medications in the CRF.

All prescription and over-the-counter medications, including vitamins and herbal supplements, that patients receive during the trial must be documented on the CRF. This documentation should continue until the patients complete the study. All medications should be evaluated to if they are prohibited or not and the appropriate action should be taken.

Concomitant medications will be coded using the World Health Organization Drug Dictionary (WHO-DD). A table of concomitant medications based on the anatomic therapeutic chemical classification (ATC) and preferred name will be produced.

6.3.11 Glucocorticoid Toxicity Index (GTI)

The GTI is a validated tool permitting investigators to assess the use of glucocorticoids and its toxicity that is relevant to patients (McDowell et al., 2020). The GTI is designed to measure change in GC toxicity between 2 points in time and includes 2 components, a Composite Index and a Specific List. The full Composite Index includes 9 domains and a total of 31 unique weighted items. Data from the GTI provide two scores:

- The Cumulative Worsening Score (CWS) – The CWS is designed to assess cumulative GC toxicity, regardless of whether the toxicity has lasting effects or is transient. New toxicities that occur are added, but toxicities that appear to resolve on follow-up are not removed. Thus, the CWS serves as a lasting record of GC toxicity that occurs. The CWS can only increase or remain the same over time.
- The Aggregate Improvement Score (AIS) – The AIS is designed to capture improvement in glucocorticoid toxicity. With the AIS, toxicities can be removed if improvement occurs (and added if worsening occurs). If an item of toxicity is present at baseline or occurs during the trial resolves over the course of follow-up, then that improvement is reflected in a negative AIS for that Item during that interval. The AIS scores improvement in GC toxicity the same as a corresponding worsening of GC toxicity.

6.3.12 Vasculitis Damage Index (VDI)

VDI is a standardized clinical assessment of damage in the systemic vasculitides (Merkel et al., 2011). The VDI consists of 64 items of damage selected by expert consensus as representative of the forms of damage developed by subjects with systemic vasculitis ([Appendix 8](#)). The VDI is that it has provided investigators with a method to ensure that items of damage are uniformly collected across centers.

6.4 Removal of Patients from the Trial or Study Drug

6.4.1 Patient Withdrawal

All patients have the right to withdraw consent and discontinue participation without prejudice at any time during the trial. Every effort should be made to comply with the protocol; however, patients will be withdrawn from the trial entirely with no further trial visits if any of the following situation arise:

- Withdrawal of patient's consent or patient's request to discontinue from the trial for any reason.
- The patient is unwilling or unable to comply with the protocol

Patients who are withdrawn from the trial will not be replaced. The reason for the patient's withdrawal from the trial should be recorded on the electronic case report form (eCRF).

6.4.2 Other Special Situations Reports

The following other Special Situations Reports should be collected even in the absence of an Adverse Event and transmitted to Genentech:

- Data related to the Product usage during breastfeeding
- Data related to overdose, abuse, misuse or medication error (including potentially exposed or intercepted medication errors)
- In addition, reasonable attempts should be made to obtain and submit the age or age group of the patient, in order to be able to identify potential safety signals specific to a particular population

6.4.3 Patient Lost to Follow-up

At the start of the study, the Investigator should try to obtain all relevant contact details for the patient to facilitate contacting the patient, if necessary. In addition, each patient should be encouraged to attend all trial visits for which the patient is scheduled.

If a patient discontinues the study without notifying the investigator, the investigator must make every effort to contact the patient to identify the reason for the patient's withdrawal and to encourage the patient to complete the applicable Early Withdrawal/End of Study visit assessments ([Appendix 1, Schedule of Events](#)). If documented attempts to contact the patient fail, and a reason for the patient's discontinuation is undiscoverable, the investigator can declare the patient as "lost to follow-up" at the end of the study. The investigator should document in the corresponding medical record all efforts to contact the patient.

6.5 Early Termination of the Trial

In the event that the trial is terminated early, the sponsor or its designee will complete the following tasks within 7 days:

- Notify all investigational sites, IRB/EC, and DSMB that the trial is terminated
- Discontinue shipment of any new investigational products to the sites, if applicable

The investigators will contact all study patients and schedule the End of Study visit promptly upon the notification that the trial has ended.

The investigator may withdraw a patient from the PRRR study for any of the following reasons:

- A protocol violation occurs,
- A serious or intolerable adverse event occurs,
- A clinically significant change in a laboratory parameter occurs,
- The sponsor or investigator terminates the study, or
- The patient requests to be discontinued from the study.

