3.1.2 Maintenance Phase

Patients who respond to treatment and achieve clinical remission will enter the maintenance phase and be evaluated every 3 months after the 6-month primary outcome assessment for a total of 18 months from the first dose. Patients will be considered treatment failures if the glucocorticoid dose has to be increased either during the prednisone taper or after remission because of a disease relapse or if any other treatment for ANCA-associated vasculitis is prescribed to treat a disease relapse. The patients who experienced treatment failure with detectable B cells (≥ 5 cells/ μ l) will be offered open-label obinutuzumab accompanied by one to three intravenous methylprednisolone pulses (1000 mg each) starting on or within 10 calendar days of obinutuzumab followed by oral glucocorticoid dosing at the discretion of the investigator (but not to exceed the original specified glucocorticoid tapering regimen) to control the disease. Patients who experience a treatment failure and B cells are still depleted should be treated according to best medical judgment. Patients who respond to the re-treatment and achieve clinical remission will enter the maintenance phase and be evaluated every 3 months until the entire study completes. Any patient who experiences treatment failure should continue with study follow-up visits per the schedule of assessments through the end of study.

All patients will be followed until they will have completed 18 months of follow-up or withdraw from the study prematurely.

The specific visit schedule is presented in Section 7, [Table 5](#). The study design is illustrated in [Figure 1](#).

[figure not shown]

Figure -1 PRRR Study Design

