5.2.2 Obinutuzumab or Rituximab

Obinutuzumab or rituximab is administered via intravenous infusion at 1000 mg per dose. Patients will receive two doses of obinutuzumab or rituximab administered on day 0 and on day 14 (\pm 2 days).

First infusion: Administer at 50 mg/hr. The rate of the infusion can be escalated in 50 mg/hr increments every 30 minutes to a maximum of 400 mg/hr.

Subsequent infusions if no adverse events with first infusion: May start at 100 mg/hour and increase at 100 mg/hour every 30 minutes to maximum rate of 400 mg/hour if no adverse events occur.

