9.7 Secondary Endpoints

No sensitivity analyses and adjustment for multiple comparisons will be conducted for the secondary endpoints. Nominal p-values will be used to examine any trends in these endpoints. The analyses will be carried out on the ITT and mITT populations, with no imputation for missing data. The secondary endpoints are:

- To compare the proportion of subjects who achieve sustained complete remission at months 6, 12 and 18 (BVAS/WG = 0 without glucocorticoids) by administration of obinutuzumab or rituximab. These comparisons will be carried out using Fisher's Exact test.
- To compare the time to treatment failure through month 18 by administration of obinutuzumab or rituximab; patients will be considered treatment failures if the glucocorticoid dose has to be increased because of a disease relapse either during the prednisone taper or after the remission is achieved. A disease relapse is defined as an increase in the BVAS/WG of 1 point or more accompanied by a decision on the part of the investigator to increase treatment for PR3-AAV. Time-to-treatment failure will be compared between treatments using the log-rank test; Kaplan-Meier plots of time to treatment failure through 18 months will be generated for each randomized treatment group; patients not experiencing treatment failure will be censored at last known follow-up for these analyses.

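### Section 6.5 lets the investigator end a patient's study participation for a serious adverse event, laboratory change or protocol violation; after about day 14 this stops no randomised drug and loses outcome data.

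*Combined protocol and SAP*

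**What the plan says.** Section 6.5 deals mainly with early termination of the whole trial, but it closes with a rule for individual patients: "The investigator may withdraw a patient from the PRRR study for any of the following reasons". Three of its five reasons are "A protocol violation occurs", "A serious or intolerable adverse event occurs" and "A clinically significant change in a laboratory parameter occurs". The other two are termination of the study and the patient's own request. The rule is discretionary, and it concerns the study, not only the drug.

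Section 6.4.1 states that "patients will be withdrawn from the trial entirely with no further trial visits if any of the following situation arise". It then gives two situations: withdrawal of consent or patient request, and unwillingness or inability to comply. Withdrawn patients are not replaced.

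On dosing, section 5.2.2 says "Patients will receive two doses of obinutuzumab or rituximab administered on day 0 and on day 14", with a ±2-day window. Section 3.1.3 confirms that the regimen is complete after the second infusion. Section 5.2.3 has separate rules for stopping an infusion or discontinuing treatment after a reaction.

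On follow-up, section 3.1.2 says "Any patient who experiences treatment failure should continue with study follow-up visits per the schedule of assessments through the end of study". No equivalent instruction covers patients with a 6.5 reason. Section 7.4 asks for the month-18 procedures at early termination but is worded for patients who withdraw consent. Section 10.10 adds another route: a major deviation prompts a decision on whether the patient remains in the study.

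On analysis, section 9.7 analyses secondary endpoints "with no imputation for missing data" and censors time to treatment failure at last known follow-up. Section 9.2 rules out sensitivity analyses for missing data.

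**The concern.** Stopping a drug and leaving a study are different events, and section 6.5 does not separate them. Once the second infusion is given, no randomised drug remains to be stopped, so a 6.5 withdrawal ends scheduled observation without changing randomised exposure.

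The patients affected are unlikely to be a random subset, because the triggers are toxicity, laboratory deterioration and departures from protocol. Some triggers can be the efficacy outcome itself. Under section 6.3.9.4, worsening vasculitis is recorded as an adverse event when it is serious. A relapse that leads to hospital admission can therefore be a treatment failure whom 3.1.2 keeps in follow-up and also a serious adverse event for which 6.5 permits withdrawal. Because the rule is discretionary, its use may also differ between the three sites.

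At stake are the month-6 estimate, the month-12 and month-18 remission proportions, the censoring assumption behind the log-rank comparison, and later safety data. The trial is exploratory, and section 9.5 says that trends in the primary rate will shape future studies. The estimate and its interval are therefore its main product.

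**Working it through.** The plan states no withdrawal rate and no figure for this rule, so there is nothing to reproduce. The check is a comparison of the text, followed by a scale calculation.

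**1. Time with no randomised drug left to stop.** Second infusion at day 14 (5.2.2); month-6 visit at day 180 (Table 5). 180 − 14 = 166 days, and 166/180 = 92% of the induction period. Follow-up then runs to day 540, a further 360 days.

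**2. What is lost, by time of withdrawal.**
- Before the second infusion: that infusion and all later outcomes.
- From about day 14 to month 6: the primary outcome and everything after it.
- After month 6: the primary outcome is already recorded; later remission status, time to failure and scheduled safety assessments are lost.

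**3. Whether the analysis repairs the loss.** Section 9.5 mentions withdrawn patients only to fix when the analysis is run; it gives no scoring rule. Sections 9.2 and 9.7 exclude the usual remedies. The 7.4 visit takes place when the patient leaves, so it does not supply a month-6 assessment.

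**4. Size.** Inputs: 30 patients allocated 1:1, so 15 per arm; anticipated rates 0.55 and 0.30 (9.2), a difference of 25 points. Numbers of withdrawals are assumptions.
- One missing outcome in an arm of 15: best minus worst = 1/15 = 6.7 points.
- One missing per arm: the risk difference ranges over 2/15 = 13 points.
- Two missing per arm: 4/15 = 27 points, more than the anticipated 25.

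**5. Example with assumed counts.** Suppose 8 obinutuzumab responders are observed, two obinutuzumab patients are withdrawn before month 6, and 5 of 15 rituximab patients respond. Newcombe continuity-corrected 95% intervals:

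| Scoring of the two withdrawn | Rates | Risk difference (95% CI) |
|---|---|---|
| Failures | 8/15 vs 5/15 | 0.20 (−0.18 to 0.52) |
| Excluded | 8/13 vs 5/15 | 0.28 (−0.12 to 0.59) |
| Responders | 10/15 vs 5/15 | 0.33 (−0.06 to 0.62) |

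With one withdrawn the estimate runs from 0.20 to 0.27; with three, from 0.20 to 0.40.

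**6. Why 6.7 points is a ceiling.** If one patient is excluded and 8 of the remaining 14 respond, the observed rate is 57.1%. The full-data rate would be 8/15 = 53.3% or 9/15 = 60.0%, an error of 3.8 or 2.9 points. With 5 of 14 (35.7%), the full-data rate is 33.3% or 40.0%, an error of 2.4 or 4.3 points. An error of 6.7 points arises only when all or none of the observed patients respond and the missing patient is the exception.

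**The case against.** The strongest reply is that 6.5 is narrower than it looks. The adverse event must be serious or intolerable, the laboratory change clinically significant, and the decision is optional. Section 10.10 reserves violations for departures from eligibility or medication rules, or those with added risk or an effect on data or outcome. This stands: minor events do not trigger the rule.

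Three stronger readings are tempting, and the documents do not support them.
- A reader might infer that 6.5 flatly contradicts 3.1.2. It does not: 3.1.2 covers treatment failures only, and failure is not a 6.5 reason. The overlap is partial, as with a relapse that is also a serious adverse event. Likewise 6.4.1 does not call its list exhaustive; it says when withdrawal is required, while 6.5 says when it is allowed.
- A reader might infer that withdrawn patients leave the primary denominator. The no-imputation statement is made for secondary endpoints. The primary set is every randomised patient who received any drug (9.3.2), and 9.5 requires success to be achieved at month 6, so counting a withdrawn patient as not meeting the endpoint is a plausible reading. The rule is simply unstated, and 9.1 leaves detail to a separate SAP. Scoring as failure would not remove the problem, because a discretionary withdrawal would then count as an efficacy failure.
- A reader might infer that all later safety information is lost. Sections 6.3.9.6 and 6.3.9.11 continue reporting of related serious events and follow-up of existing adverse events. What is lost is scheduled assessment and, after the collection period in 6.3.9.4, new non-serious events.

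It is also fair that a withdrawal before the second infusion does stop randomised drug.

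**Conclusion.** The point holds as a should-fix matter of design wording. For withdrawals after the second infusion, section 6.5 permits loss of outcome data that serves no purpose in stopping randomised drug, may be related to outcome, and is not repaired by the analysis as written. The size is at most 6.7 points of uncertainty in an arm's rate per missing month-6 outcome. Two per arm would span more than the anticipated effect. These figures rest on 15 patients per arm and assumed numbers of withdrawals; if nobody is withdrawn under 6.5, nothing is lost. The harm is to the estimates and their intervals. Section 9.2 already says that the trial is not powered for superiority, so no power claim is affected.

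**What to change.** Reconcile sections 6.4.1, 6.5, 7.4 and 10.10 so that discontinuing study drug and leaving the study are separate events. State that an adverse event, laboratory change or protocol violation does not by itself end scheduled follow-up and outcome collection to month 18. Participation would end early when the patient withdraws consent, is unable or unwilling to comply, or is lost to follow-up. Word 7.4 to cover every early departure, and record the reason and date of each. In section 9.5 or the SAP, state how a patient without a month-6 outcome is scored.

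Leave the infusion-stopping rules and all clinical management as they are.

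The cost is a wording amendment and a few retained visits that are already on the schedule. The planned sample size and analyses are otherwise unchanged.

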6.6 Dispensing Study Drug

The study drug for infusion will be prepared by the site pharmacist who has access to the randomization schedule following the procedures in [the Pharmacy Manual](#).

7 STUDY ACTIVITIES

The study activities at each clinic visit listed below are presented in [Schedule of Events](#) and [Schedule of Laboratory Testing](#). Detailed study procedures are described in [Section 6](#).

A visit window is allowed for all visits except visit V2. Visit 2 is the first day of dosing and the basis for the visit window.

Table 5 Study Visit Schedule

Visit No.	Visit	Study Day	Visit Window
1	Screening	Varies	Before baseline visit (up to 14 days prior to the baseline visit)
1a	IV steroid #1	G1	Within 10 days of baseline up to day of baseline (V2)
1b	IV steroid #2	G2	Optional, Within 24 hours after IV steroid 1
1c	IV steroid #3	G3	Optional, within 24 hours after IV steroid 2
2	Infusion 1 (Baseline)	0	Within 14 days from screening
3	Infusion 2	14	±2 days of the targeted date
4	Month 1	30	± 2 days of the targeted date
5	Month 2	60	±3 days of the targeted date
6	Month 4	120	±5 days of the targeted date

7	Month 6	180	±10 days of the targeted date
8	Month 9	270	±10 days of the targeted date
9	Month 12	360	±10 days of the targeted date
10	Month 15	450	±10 days of the targeted date
11	Month 18	540	±10 days of the targeted date
99	When disease flares	unscheduled	

7.1 Screening Visit V1 (Up to 14 days Before Day of Randomization)

- Explain the content of the informed consent materials to the patient and collect signed informed consent
- Collect needed information and evaluate conformance to inclusion and exclusion criteria
- Obtain Demographic Information
- Obtain medical history including AAV disease history
- Record pre-treatment medications
- Record current glucocorticoid use
- Measure vital signs, including blood pressures, pulse, and temperature
- Perform a 12-lead ECG measurement
- Complete the BVAS/WG Score
- Complete the VCRC-Disease activity and Transition Assessment by the investigator
- Draw blood for clinical laboratory tests. The specific laboratory tests scheduled for this visit are listed in [Appendix 2](#)
- Collect a clean-catch, mid-stream urine sample for urinalysis

7.2 Remission Induction Period (Day 0 to Month 6)

7.2.1 Pre-Treatment of Methylprednisolone

Eligible patients will start the one to three pulses of glucocorticoid of methylprednisolone starting on or within 10 calendar days of study day 0 (1000 mg each, iv infusion). The initial treatment with methylprednisolone may start while data for eligibility confirmation are pending. If their first RTX/OBI infusion coincides with one of the methylprednisolone pulses of 1000 mg, then the patient can receive the 1000 mg of methylprednisolone as their pre-RTX/OBI glucocorticoid infusion. If the patients have already completed the one to three methylprednisolone pulses, they will receive only 60 mg of methylprednisolone before the rituximab or obinutuzumab infusion that day. The pre-RTX/OBI treatment with methylprednisolone may be substituted with the IV pulse for one of the pre-treatment infusions.

7.2.2 Visit 2 (Day 0) Procedures

- Confirm the subject eligibility
- Perform randomization procedures (The randomization procedure may start the day before the scheduled Day 1 visit by the pharmacist. The dosing solution must be prepared within 24 hours of scheduled dosing.)
- Record vital signs, including blood pressures, pulse, and temperature prior to infusion
- Complete the BVAS/WG Score prior to infusion
- Complete the VCRC-Disease activity and Transition Assessment by the investigator
- Review glucocorticoid use prior to infusion
- Complete AAV-PRO by the patients prior to infusion
- Complete GTI assessment prior to infusion
- Complete VDI assessment prior to infusion
- Draw blood for clinical laboratory tests prior to infusion
- Collect samples for mechanistic biomarker assessments prior to infusion
- Collect a clean-catch, mid-stream urine sample for urinalysis prior to infusion
- Assess adverse events prior to, during and after infusion
- Record medications used prior to, during and after infusion
- Administer study drug infusion and observe for 2 hours after infusion is complete

7.2.3 Visit 3 (Day 14 ± 2 days) Procedures

- Record vital signs, including blood pressures, pulse, and temperature prior to infusion
- Complete the BVAS/WG Score prior to infusion
- Complete the VCRC-Disease activity and Transition Assessment by the investigator
- Draw blood for clinical laboratory tests prior to infusion
- Collect a clean-catch, mid-stream urine sample prior to infusion
- Record medications used prior to, during and after infusion
- Review glucocorticoid use prior to infusion
- Assess adverse events prior to, during and after infusion
- Administer study drug infusion and observe for 2 hours after infusion is complete

7.2.4 Visit 4 (1 month after the first infusion) Procedures

- Draw blood for clinical laboratory tests (during clinic visit only)
- Collect a clean-catch, mid-stream urine sample for urinalysis (during clinic visit only)
- Collect samples for mechanistic biomarker assessments
- Complete the BVAS/WG Score

- Complete the VCRC-Disease activity and Transition Assessment by the investigator
- Record medications used
- Review glucocorticoid use
- Assess adverse events

